• Describe predictors of interest along with potential confounders and effect modifiers Predictors of interest include drug abuse history and/or behavior, as well as anticipated benefit from history of medication usage in the literature. Potential confounders include previous narcotic use history, narcotic tolerance/dependence in patients not otherwise excluded during recruitment, variable pain thresholds and tolerance amongst different patients, duration and complexity of surgeries, as well as variable renal clearance. Many of these are also effect modifiers.

• Describe matching criteria, if applicable

Matching criteria will not be used at this study will be structured as a randomized control trial.

• Describe duration of follow-up, and timing of data collection

Post-operative imaging will be reviewed to determine successful decompression and instrumentation. Data collection will be done during patient's hospital stay. Patients will be asked about their post-operative pain at 4 hour intervals, and data regarding their overall narcotic usage and their time to ambulation will be recorded from the medical record. Follow-up will then consist of: 1 week for phone call by spine NP, 2 week evaluation as is standard for all post-operative patients.

• Describe the planned interventions and their timing.

A study participant will be randomized ahead of time to be administered methadone or the current standard of care in blocks of 5 blinded to clinical personnel. If the patient is assigned to the methadone group, the anesthesiology team will be given this information and the anesthesiologist assigned to the Revised 4/17/13, 6/23/15

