case and will administer a 0.2 mg/kg single-dose administration of methadone on incision (not to exceed 20 mg, as used in the literature) with a ketamine infusion of 4 µg/kg/min and a remifentanil infusion starting at 0.1 µg/kg/min and titrating to effect or sufentanil infusion starting with a dose of 0.3 µg/kg/hr and titrating to effect. These standard doses have been well documented and studied in the literature as demonstrated above and will be overseen and have been approved by board certified anesthesiologist. For lengthier procedures, there will not be re-dosing of narcotics toward the end of the procedure. The operative procedure will not be altered in any way for the purposes of this study, and is beyond the scope of this protocol, yet can be detailed as requested. The patient will be taken to the recovery room postoperative and will be put on a standard post-operative morphine PCA as used in our department at a rate of 1mg per 6 minute lock-out period. This standard dose and therapy has been used in nearly all postoperative lumbar fusion patients to date. Patient's narcotic usage and pain rating will be recorded at the intervals listed above and when stable from a cardiovascular standpoint, will be transition to the neurosurgery floor. Once able to bare weight, the patient will be encouraged to work with physical and occupational therapy as per standard post-operative protocol. One the patient uses the PCA at a rate of less that once an hour, and can be managed with oral pain medications, the PCA will be removed. The remainder of their post-operative care will be according to the standard departmental protocol, and when milestones such as ambulation, voiding, and pain control are met, they will be discharged either to home, an acute care facility, or a subacute rehabilitation center. Per standard of care, the patients will return to the clinic at 2 weeks and 3 months as part of their routine clinical care. Any adverse events/reactions will be recorded and managed as normally they would be, and naloxone will be available for suspicion of narcotic overdose. Patient assigned to the control group will be monitored in the manner post-operatively, as is the standard of care for all of our patients.

Define the outcome measures pertaining to each aim.

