The sample size was determined using the Gottschalk study listed in the reference section which used methadone vs. sufentanil in 29 patients undergoing lumbar fusion surgery and the measures for pain level and total narcotic usage at 48 hours to determine an 'n' for the total study population, using a power of 0.80. The details of the calculations is listed in the data analysis section (7a) below and calculated with the suggestion of the statistician on the IRB. The assumptions with which the outcomes are hypothesized are the result of previously published data using similar populations. Two sample t-tests are appropriate to determine statistical significance between mean pain scores between different patients in the control and study groups for each individual time point as there will be no censoring of the study data. Ranked T-test may also be used if outliers are present, however patients with unusual post-operative courses may be excluded if their reason for prolonged hospitalization is unrelated to immediate post-operative pain

control. The large sample size plans to take into account possible outliers that may not be included in final analysis, despite their mention in study write-up to determine why their post-operative hospitalization was prolonged. Additionally, data about patients' mean time to ambulation, mean time to discharge, and mean overall narcotic usage will be measured between the control and study populations. Data analysis will be performed with the assistance of the biostatistician listed as a member of the study team, [name], from the Albert Einstein College of Medicine, Division of Biostatistics. Thus, a sample of 60 completed methadone patients will be evaluated against 60 randomized, standard narcotic regimen controls. The mean data for control patients' pain ratings, narcotic usage, time to ambulation, and time to discharge will be obtained, the statistical deviation of this data will be measured and compared to subject data in all facets.

• Take into account anticipated drop-out or loss-to-follow up rate.

We intend to screen 200 patients to have 60 in each arm ultimately included in the study. Since the intervention is a single intra-operative occurrence, that when completed patients cannot reverse, we do not anticipate any drop-out. A two week follow-up visit is a required standard of care for all post-operative patients, without patient loss to follow-up historically. The study is completed at this point.

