Two sample T-tests will be performed to evaluate continuous variables such a total morphine dose, pain level per VAS, time to first morphine dose, time to ambulation, and time to discharge. The assistance of a statistician, [name], from the Albert Einstein College of Medicine, Division of Biostatistics will be used for statistical analyses performed in this study. Wilcoxon Rank Sum Test will be used if outliers are noted in the study population, detected as more than 5 MAD from the median, and a concern presents that single patients may skew the data. Additionally, review of these patients who are outliers may also necessitate their exclusion from this work if they provide data that will significantly modify the mean of the remaining patients. This can be accounted for in the goal of 60 patients to be accrued in each arm of the study. A thorough explanation and review will performed on any such patients in any form of write up of this work.

At least one study hypothesis (or a statement that the study is hypothesis-generating or a feasibility study):

The use of single dose intraoperative methadone will decrease total narcotic usage, time to ambulation, mean pain rating at 24 and 48 hours and will decrease number of days of hospitalization compared to sufentanil (current standard of care) controls.

• A statement regarding specifically what data are to be used to test the hypothesis (or to generate the hypotheses)

We will obtain data of total narcotic usage, days until patients ambulate with physical therapy, pain ratings at 24 and 48 hours, and days to discharge, all obtained from the patient's medical record.

- o The statistical method(s) to be used to test the hypothesis with that data
 Two-sample T-test will be used with the assistance of an Albert Einstein statistician, [name], to analyze
 the above data and determine if there is statistical significance between the two groups, in addition to the
 stipulations outlined above to address outlier patients.
- A power analysis to determine the sample size (even for pilot studies)

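### The no-censoring premise fails for 48-hour pain: patients discharged earlier have no planned score, and the missing scores are related to pain

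*Combined protocol and SAP*

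**What the plan says.** The sample-size item in Section 3 plans two-sample t-tests on mean pain "for each individual time point as there will be no censoring of the study data". Section 7(a) states the hypothesis in terms of "mean pain rating at 24 and 48 hours and will decrease number of days of hospitalization", and names as its data "pain ratings at 24 and 48 hours, and days to discharge, all obtained from the patient's medical record".

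On collection, the follow-up item in Section 2 says "Data collection will be done during patient's hospital stay" and "Patients will be asked about their post-operative pain at 4 hour intervals". It continues: "Follow-up will then consist of: 1 week for phone call by spine NP, 2 week evaluation". The research-material item in Section 3 adds that nothing needs to be obtained specially for the study.

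On discharge, the interventions item in Section 2 says that "when milestones such as ambulation, voiding, and pain control are met, they will be discharged". Sections 2 and 7(a) both hypothesise a shorter stay with methadone.

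The loss-to-follow-up item in Section 7 allows data that are complete up to discharge to be used. No section gives a rule for a missing 24-hour or 48-hour score, a repeated-measures model or a sensitivity analysis. The outcome list in Section 2 places subjective pain control among the secondary outcomes.

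**The concern.** The plan predicts shorter stays, yet its pain analysis assumes that every patient is still in hospital to be scored. A t-test at 48 hours uses only those who remain. Since pain control is one condition for leaving, those who remain will tend to have more pain than those who left. If early discharge is more common with methadone, the comparison is between groups selected after treatment, and the methadone arm loses more of its low-pain patients. A real benefit at 48 hours could then be diluted.

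A second issue is how many pain tests there are. Section 3 speaks of every time point; Section 7(a) names two. The chance of a false positive depends on which is meant.

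**Working it through.** **1. The plan's own figure.** Inputs from Section 7(a): effect 0.56 SD, power 0.80, alpha 0.05, taken as two-sided because that reproduces the figure. n per group = 2 × ((1.960 + 0.842)/0.56)² = 50.06, rounded up to 51, as stated. With 60 per group the power at 0.56 SD is 86%. The arithmetic is sound but needs a value from every patient. Since 51/0.85 = 60, the margin covers at most 15% missing, and only if missingness is unrelated to pain. Sections 3 and 7(a) already assign that margin to excluded outliers.

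**2. Is a 48-hour score planned after discharge?** Pain is asked about in hospital, the source is the chart, and the next contacts are at 1 and 2 weeks. So no.

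**3. Bias of the 48-hour t-test.** Assumptions, not in the documents: pain and readiness to leave are jointly normal, the correlation between low pain and early discharge is ρ = 0.5, SDs are equal, and there is no true pain effect. If a fraction p has left, the mean pain of those remaining is raised by ρ × λ(p) SD, where λ(p) = φ(Φ⁻¹(p))/(1 − p). The bias is ρ × [λ(p methadone) − λ(p control)].

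λ(0.10) = 0.195; λ(0.15) = 0.274; λ(0.20) = 0.350; λ(0.30) = 0.497; λ(0.40) = 0.644.

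| Gone before 48 h, control vs methadone | Bias against methadone |
|---|---|
| 10% vs 15% | 0.5 × (0.274 − 0.195) = 0.04 SD |
| 10% vs 20% | 0.5 × (0.350 − 0.195) = 0.08 SD |
| 20% vs 30% | 0.5 × (0.497 − 0.350) = 0.07 SD |
| 10% vs 30% | 0.5 × (0.497 − 0.195) = 0.15 SD |
| 20% vs 40% | 0.5 × (0.644 − 0.350) = 0.15 SD |
| equal in both arms | 0 |

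A simulation of 20,000 trials with 60 per arm agrees. At 10% vs 30% with no true effect, the two-sided type I error is about 12%, almost all of it against methadone. With a true benefit of 0.56 SD:

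| Gone before 48 h, control vs methadone | Observed benefit | Power |
|---|---|---|
| none | 0.56 SD | 86% |
| 5% vs 10% | 0.52 SD | 80% |
| 10% vs 20% | 0.48 SD | 71% |
| 10% vs 30% | 0.41 SD | 54% |

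**4. How many leave before 48 hours?** Section 7(a) gives an SD of stay of 6.7 days but no mean. For illustration, take a lognormal stay with mean m: s² = ln(1 + (6.7/m)²), μ = ln m − s²/2, and the share under 2 days is Φ((ln 2 − μ)/s). This gives about 35% at m = 5 days, 6% at 8 days and 1% at 10 days. The problem could be material or negligible.

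**5. Number of tests.** Each test is at two-sided 5%. For the two time points in Section 7(a), familywise error = 1 − P(|Z₁| ≤ 1.96 and |Z₂| ≤ 1.96), which is 9.1% at correlation 0.5 and 7.0% at 0.9. If all 48/4 = 12 scores were tested, simulation gives about 14% (equal correlation 0.9) to 32% (equal correlation 0.5), and 21% to 41% when correlation decays with time (0.9 to 0.5 between neighbouring scores).

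**The case against.** The strongest reply concerns scale. Early discharge before 48 hours may be rare; the documents do not say. A treatment effect on discharge is a hypothesis, and pain control is only one milestone beside ambulation and voiding. Equal early discharge leaves the comparison unbiased under the assumptions above. Pain is a secondary outcome, and narcotic dose, ambulation and length of stay do not have this gap. All of that stands. It limits the size of the problem but does not supply a 48-hour score or a rule for its absence.

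Three stronger readings are tempting, and the documents do not support them.

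- A reader might infer that methadone will empty its arm of comfortable patients. The plan hypothesises earlier discharge; it does not establish it.
- A reader might infer a bias of about 0.23 SD. With ρ = 0.5 that needs 30% of controls and 60% of methadone patients gone before 48 hours, and nothing in the documents points to such rates.
- A reader might infer a false-positive chance of 20 to 30% or more for pain. That requires 12 separate confirmatory tests. Section 3's wording permits that reading, but Section 3 refers to Section 7(a) for the details of its calculations, and the hypothesis there names only two time points.

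**Conclusion.** The no-censoring premise does not hold for 48-hour pain, and nothing else in the plan repairs it: the loss-to-follow-up item does not deal with patients who are discharged on schedule. Strictly, the problem is missing data rather than censoring.

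That the missing scores are related to pain follows from the discharge milestones. Bias between arms requires, in addition, unequal early discharge, which is what the trial expects. Its direction is then against methadone, so the main risk is a diluted benefit rather than a false one. The sizes rest on the assumed correlation and early-discharge rates. The 24-hour comparison should be less affected.

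The wording on time points in Sections 3 and 7(a) should be reconciled. This should be corrected, but it does not threaten the trial's other outcomes.

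**What to change.** - Delete the no-censoring statement as it applies to pain.
- Replace the separate t-tests with one mixed model for repeated measures on the 4-hourly scores to 48 hours, with arm, time and arm by time. Include pre-operative pain only if it is in the chart; the plan does not show that it is collected. Take the 24-hour and 48-hour contrasts from this model, so that patients who leave early contribute their earlier scores. State the covariance structure in advance.
- State in Sections 3 and 7(a), in the same words, which pain time points are tested.
- Report by arm how many patients have a 48-hour score.
- Add a not-at-random sensitivity analysis for patients discharged before 48 hours, for example by shifting their modelled 48-hour pain over a stated range in each arm.

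The cost is revised wording and modest extra analysis of scores already planned. The downside is reliance on a missing-at-random assumption: given the scores already recorded, leaving must not depend further on the unseen 48-hour score. That cannot be verified, but it is weaker than what the complete-case t-test needs, and the sensitivity analysis tests how much depends on it.

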In another series, three groups of methadone vs. morphine vs. placebo for the treatment of pain in cardiac surgery patients were used, and the methadone group had equivalent anesthetic times, required lower narcotic doses, had longer latencies to fist analgesic dose, had better pain control, and had lower incidences of nausea and vomiting compared to all other groups. 10 The authors speculated that the decreased nausea and vomiting was due to the overall lower narcotic doses post-operatively. Methadone patients required fewer additional post-operative analgesic administrations, on average less than 1 additional dose, and morphine and control patients required significantly more.

In a series of 156 cardiopulmonary bypass patients randomized to receive either fentanyl of methadone, the quality of pain management was rated better by the patients in the methadone group and there was no greater opioid-related adverse events compared to controls.⁶ Patients used smaller equivalent narcotic doses in the methadone group (40% less in the first 24 hours) and had nearly twice as long times to first rescue dose. Of the few patients in this series who required no additional narcotic dosing (5), they were all in the methadone group.

In a series of 31 children who were administered single-dose intraoperative methadone for scoliosis repair, doses of up to 20mg were tolerated well and pharmacokinetic profiles were followed for 96 hours.⁴ Pharmacokinetics in children were similar to those for methadone in adults. There was no difference between methadone patients and control patients receiving equivalent doses of morphine, hydromorphone, fentanyl, sufetanil and oxycodone in regards to adverse events including respiratory depression, decreased oxygen saturation, or altered mental status. Post-operative PCA use was lower in the methadone group, however this difference did not reach statistical significance, possibly because, as the authors speculate, the dose of methadone being small compared to the overall narcotic dose. Children in the methadone group also reported overall greater comfort in the recovery room as compared to their cohort controls.

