In another series of spinal fusion patients administered 20mg methadone intra-operatively and 5mg doses as needed post-operatively in the recovery room (1-3 doses), there was little variability in methadone blood concentration in patients with adequate pain control, suggesting a dose-dependent effect.8 Mean half-life was 21±13hours with a range of 5-48 hours, with a VAS rating of 1.5±1.3 with adequate pain control. A repeat dose of methadone (i.e. 2.5, 5, or 10 mg iv) in the recovery room provided sufficient pain control for the remainder of the hospitalization for some patients in this cohort. The 2.5mg dose was associated with an average additional 7.4h of pain control, while the 5 and 10mg doses were associated with 9.6h of pain control. In another study cited in this report, 40% of surgical patients required no additional post-operative pain control after a single 20mg iv methadone dose intra-operatively, and the 35% that did require a single additional dose required it on average 18.4±6.6 hours post-operatively. The remainder received additional non-narcotic pain medications post-operatively which were sufficient to control pain to tolerable levels.

In one of the first series of methadone use in patients undergoing lumbar fusion surgeries, 22 patients were divided into two treatment arms with one group of patients receiving methadone only and the other receiving methadone plus ketamine.⁵ While there was no difference in pain rating post-operatively, the ketamine plus methadone group used significantly less methadone (70%) than the other control groups. This finding suggests that intra-operative co-administration of ketamine may potentiate the effects of methadone. To keep consistent with this data and to demonstrate a narcotic minimizing plan that sufficiently controls patients' pain, ketamine will included in this proposed protocol, as it is already a medication used for the analgesia of patients undergoing this surgical procedure.

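### Time to first morphine dose is given a t-test with no rule for patients who never take morphine; omitting them would bias this one unlisted comparison against methadone

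*Combined protocol and SAP*

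**What the plan says.** Section 7(a) names the test and the variable together: "Two sample T-tests will be performed to evaluate continuous variables such a total morphine dose, pain level per VAS, time to first morphine dose". This is the only place where time to first morphine dose appears. It is not among the primary or secondary outcomes in section 2, the hypothesis in section 7, the power calculation or the interim measures.

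No section gives a value, rank or censoring time to a patient with no morphine dose. Two neighbouring rules in section 7(a) bear on the variable without filling that gap:

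- The fallback: "Wilcoxon Rank Sum Test will be used if outliers are noted in the study population, detected as more than 5 MAD from the median". It is triggered by outliers and does not place non-users.
- The exclusion rule: outlying patients may be reviewed, which may "necessitate their exclusion from this work if they provide data that will significantly modify the mean of the remaining patients". A very long time to first dose could meet it.

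Section 3 justifies t-tests "as there will be no censoring of the study data", in a sentence about mean pain scores at single time points.

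Section 1 reports patients who needed nothing further after methadone. On the cardiac trial: "Of the few patients in this series who required no additional narcotic dosing (5), they were all in the methadone group". On a surgical study: "40% of surgical patients required no additional post-operative pain control after a single 20mg iv methadone dose intra-operatively". The cardiac trial's methadone patients also "had nearly twice as long times to first rescue dose".

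**The concern.** After surgery every patient has a morphine PCA (section 2), so a dose is recorded only if the patient asks for one. A patient who never does has no event time, and that absence is the outcome methadone is meant to produce. A t-test needs a number, so the analyst must either drop the patient or pick a value that the plan does not give.

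Dropping non-users compares only patients who needed morphine, a group formed after randomisation and possibly shaped by treatment. The randomised contrast is lost for this variable, and any benefit that consists of avoiding morphine disappears from it. Picking a value once the data are visible leaves the result open to choice. The exclusion rule could act in the same direction by removing the longest times.

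**Working it through.** **The plan's own figure.** Section 7 gives 51 per group for 0.56 SD, 80% power and alpha 0.05. Two-sided: 2 × (1.960 + 0.842)² / 0.56² = 50.1, rounded up to 51. It reproduces, but it is a generic t-test figure. The plan has no mean, SD or target difference for time to first morphine dose, so what follows rests on assumptions.

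**Non-user rate.**
- Cardiac trial (section 1): 5 of 156, all on methadone. Arm sizes are not given; assuming 78 each, 5/78 = 6.4%, or 60 × 0.064 ≈ 4 of 60 here. Fisher's exact test of 5/78 against 0/78 gives p = 0.06.
- Surgical study (section 1): 40%, or 24 of 60. No comparator rate is given.
- Control rate here: unknown; 0% and 5% are used.

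**Lost numbers alone.** Dropping 6.4%, 20% or 40% leaves about 56, 48 or 36 methadone patients. Against 60 controls, t-test power at 0.56 SD falls from 86% to 85%, 82% or 75%. The greater effect is selection.

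**Model 1: non-use independent of latency.** 60 per arm, log-normal times with log-SD 1, control median 2 h (assumed), non-users censored at 48 h, 1,500 to 4,000 simulated trials per scenario. Power is two-sided p < 0.05 in methadone's favour. Monte Carlo standard error is at most √(0.25/1500) = 1.3 points; ranges cover repeat runs.

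| Non-users, methadone / control | Users' latency ratio | t-test, users only | Log-rank, all patients |
|---|---|---|---|
| 20% / 0% | 1.0 | 2–3% | 88–90% |
| 40% / 0% | 1.0 | 2–3% | >99% |
| 20% / 5% | 1.0 | 2–3% | 56–58% |
| 40% / 5% | 1.0 | 2–3% | 99% |
| 20% / 0% | 1.5 | 40–41% | 99% or more |
| 6.4% / 5% | 2.0 | 80–84% | 76–77% |
| 20–40% / 0–5% | 2.0 | 75–83% | 99–100% |

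At ratio 1.0 the t-test only returns its false-positive rate: 2–3% in one direction, 4–5% if both directions are counted.

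**Same idea with exponential times** (control mean 4 h, no control non-users, equal latency, censoring at 72 h). At 6.4%, 20% and 40% methadone non-users, log-rank has 21%, 88% and 100%; rank-sum with non-users last has 9%, 48% and 98%; the users-only t-test has 4–5% throughout.

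**Model 2: the longest latencies become the non-users.** Exponential times, mean 8 h on methadone and 4 h in control; anyone whose time would pass a cut-off L never takes a dose. For a methadone non-user share q, L = −8 ln q, and the control share is exp(−L/4) = q². The mean among users is μ − L × p/(1 − p), where p is that arm's non-user share. At q = 0.40, L = 7.33 h:
- Methadone: 8 − 7.33 × 0.40/0.60 = 3.1 h.
- Control: 4 − 7.33 × 0.16/0.84 = 2.6 h.

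A true difference of 4 h shows as 0.5 h. Power at q = 6.4%, 20% and 40% is 85%, 54% and 23% for the users-only t-test, 96%, 94% and 90% for log-rank, and 90%, 89% and 87% for rank-sum with non-users tied last.

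**The case against.** The strongest reply is that this is an auxiliary variable, named once in a list of examples. Opioid sparing is measured by total narcotic dose and frequency of use, both primary in section 2, where a non-user scores zero and stays in. That stands. A reader might infer that the trial's whole rescue-sparing result is biased; the documents do not support it.

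Three other inferences also go too far:

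- That the plan orders non-users to be discarded. It is silent; omission is the likely default, and an unstated value is the alternative.
- That the cited literature shows non-users falling in the methadone arm. Only the cardiac trial does, on 5 patients. The 40% has no comparator, and neither figure comes from fusion patients on a morphine PCA.
- That the plan denies censoring for this variable. The section 3 sentence is about pain scores.

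On size, the contrast of 2–3% with 88–90% assumes that methadone does not delay the first dose among users. The ratio cited in section 1 is nearly 2, and there the users-only t-test keeps most of its power; at 6.4% versus 5% non-users log-rank does no better. With such skewed times at least one value would lie beyond 5 MAD in about 99% of trials, so the planned Wilcoxon test would usually be available, and on users only it has 88–96% power at ratio 2.0. All of this stands as a limit on size. It does not remove the gap: a users-only Wilcoxon test also misses the effect when users' latencies are equal, and either users-only test answers a question about a group selected after randomisation.

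**Conclusion.** The point holds for this one analysis. The plan assigns a t-test to a variable that is undefined for patients who never take morphine, its own background leads one to expect some of them after methadone, and no rule covers them. If they are omitted, the comparison is no longer randomised and leans against methadone.

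The size cannot be fixed from the documents, because the non-user rate in this population is unknown. Under Model 1 the choice of test is immaterial near 6% versus 5%. At 20–40% methadone non-users the loss runs from moderate (75–83% against 99–100%, latency doubled) to near total (about 2–5% against 56–100%, equal latency). Model 2 lies between, with the t-test falling to 23% at 40%. The near-total figures are a worst case, not a forecast.

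The listed outcomes and the sample size are not affected.

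**What to change.** In section 7(a), take time to first morphine dose out of the t-test list and state one analysis that keeps all randomised patients. Either of these will do:

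- Kaplan-Meier curves and a log-rank test, with non-users censored at one fixed, pre-specified time. Discharge should not serve as the censoring time, since under section 2 it depends partly on pain control.
- The Wilcoxon rank-sum test that is already planned, with non-users ranked last.

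Log-rank is the stronger of the two when the benefit is mainly avoidance of morphine. Report the number per arm with no post-operative morphine, and state that the outlier-exclusion rule does not apply to long times. Keep the endpoint as first morphine dose. In section 3, limit the statement about censoring to pain scores.

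The cost is a few sentences, with no new data, since the plan already takes narcotic use from the medical record. The result becomes a curve or a rank comparison instead of a difference in mean hours.
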